## **7.5.2. Presentation of Pharmacokinetic Data**

All PK concentrations and parameters will be listed.

Summary tables, arithmetic mean (+ standard deviation [SD]) figures, overlaying individual figures, and individual figures by treatment and time postdose will be provided for plasma PK concentrations. All figures will be produced on both linear-linear and linear-logarithmic scales, with the exception of figures across all days, which will be produced on the linear-linear scale only. The  $+SD$  bars will only be displayed on the linear-linear scale.

Summary tables by treatment will be provided for all PK parameters, with the exception of diagnostic regression-related PK parameters.

A subject may be excluded from the PK summary statistics and statistical analysis if the subject has an AE of vomiting that occurs at or before 2 times the median  $t_{max}$ .

If the actual time of sample collection deviates from the nominal time by more than  $\pm 10\%$ , the plasma concentration will be flagged and excluded from the summary statistics.

Individual concentrations deemed to be anomalous will be flagged in the listings and excluded from the summary statistics.

For plasma concentration data the following rules will apply:

- Values that are BLQ will be set to 0 for the calculation of summary statistics.
- Arithmetic mean or median values that are BLQ will be presented as 0.

For PK parameters the following rule will apply:

- Geometric mean and coefficient of variation will not be calculated for  $t_{last}$  or  $t_{max}$ .

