Appendix 6: Schedule of Assessments

Schedule of Assessments – Part A (Single Ascending Dose)

Visit Name	Screening	Check-in	Treatment period			Follow-up ^a	Early termination (if applicable)	Comment (*)
Visit No.	1		2			3		
Day No. Visit window (calendar days)	-35 to -2	-1	1	2	3	8 (±2 days)		
Trial population and eligibility								
Informed consent*	X							The ICF must be signed prior to performing any protocol-related procedures, including, but not limited to, screening evaluations.
Subject eligibility	X	X						
Demographics	X							
Medical history	X							
Height and weight	X							
Alcohol breath test	X	X						
Urine drug screen	X	X						
Serology*	X							Hep B surface antigen, hep C virus antibody, HIV antibodies.
Quantiferon™ TB Gold test	X							
Serum pregnancy test*	X							All females.
FSH*	X							All females.
Trial residency								
Check-in		X						
Check-out					X			
Nonresidential visit	X							
Treatment and randomization								
Concomitant medication and concurrent procedures	X	X	X	X	X	X		
Randomization			X					
IMP administration*			X					Subjects will be dosed in a fasted state.
Safety assessments								
Physical examination*		X			X		X	Full physical examination performed at check-in. Symptom-directed physical examination at all other times.

Visit Name	Screening	Check-in	Treatment period			Follow-up ^a	Early termination (if applicable)	Comment (*)
Visit No.	1		2			3		
Day No. Visit window (calendar days)	-35 to -2	-1	1	2	3	8 (±2 days)		
Vital signs	X	X	X*	X*	X*		X	Day 1: Predose (triplicate), 1, 2, 4, 6, 8, and 12 hours postdose. Day 2: 24 hours postdose. Day 3: 48 hours postdose. Timepoints may be adjusted based on emerging data.
Safety ECG	X	X	X*	X*	X*		X	Day 1: Predose (triplicate), 2, 4, and 8 hours postdose. Day 2: 24 hours postdose. Day 3: 48 hours postdose.
Telemetry/continuous ECG*			X*	X*				See footnote b. Day 1: 3 readings predose (-60, -45, and -30 minutes), 0.25, 0.5, 1, 1.5, 2, 3, 4, 6, 8, and 12 hours postdose. Day 2: 24 hours postdose.
All hematology, coagulation, and clinical chemistry	X	X		X*	X*		X	Day 2: 24 hours postdose. Day 3: 48 hours postdose.
Urinalysis	X	X			X*		X	Day 3: 48 hours postdose.
Urine pregnancy test*		X			X		X	Only female subjects.
Adverse events	X		X			X	X	
PK/PD assessments								
PK blood sample*			X*	X*	X*		X	See footnote c. Day 1: Predose, 0.25, 0.5, 1, 1.5, 2, 3, 4, 6, 8, and 12 hours postdose. Day 2: 24 and 36 hours postdose. Day 3: 48 hours postdose.

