Weight	X	X										X	X	X	
Safety ECG	X	X	X*		X*		X*		X*	X*	X*	X	X	Day 1: Predose (triplicate), t_{max}^a . Days 3 and 5: Predose. Day 7: Predose, t_{max}^a . Day 8: 24 hours post Day 7 dose. Day 9: 48 hours post Day 7 dose.	

Visit Name	Screening	Check- in	Treatment period									Follow-up	Early Termination (if applicable)	Comment (*)
Visit No.	1		2									3		
Day No. Visit window (calendar days)	-35 to -2	-1	1	2	3	4	5	6	7	8	9	14 ±3 days		
All hematology, coagulation, and clinical chemistry	X	X		X*		X*			X*		X*	X	X	Day 2: 24 hours postdose (collected prior to dose on Day 2). Days 4 and 7: Predose. Day 9: 48 hours post Day 7 dose.
Urinalysis	X		X*		X*			X*		X*	X*	X	X	Days 1, 4, and 7: Predose. Day 9: 48 hours post Day 7 dose.
Urine pregnancy test*		X										X	X	Only female subjects.
Adverse events	X		X									X	X	
PK/PD assessments														
PK blood sample*			X*	X*	X*	X*	X*	X*	X*	X*	X*	X		See footnote b. Day 1: Predose, 0.25, 0.5, 1, 1.5, 2, 3, 4, 6, 8, and 12 hours postdose. Day 2: 24 hours postdose. Days 3 through 6: Predose. Day 7: Predose, 0.25, 0.5, 1, 1.5, 2, 3, 4, 6, 8, and 12 hours postdose. Day 8: 24 hours post Day 7 dose. Day 9: 48 hours post Day 7 dose.
CCI [REDACTED]			X*						X*	X*	X*			See footnote c. Day 1: Predose (spot collection), 0-8, 8-16, and 16-24 hours postdose. Day 7: 0-8, 8-16, and 16-24 hours postdose. Day 8: 24-36 hours post Day 7 dose. Day 9: 36-48 hours post Day 7 dose.

Visit Name	Screening	Check- in	Treatment period									Follow-up	Early Termination (if applicable)	Comment (*)
Visit No.	1		2									3		
Day No. Visit window (calendar days)	-35 to -2	-1	1	2	3	4	5	6	7	8	9	14 ±3 days		
CCI [REDACTED]				X*		X*			X*	X*	X*			Day 1: Predose. Day 4: Predose (analyzed as part of scheduled hematology and clinical chemistry evaluations). Day 7: Predose (analyzed as part of scheduled hematology and clinical chemistry evaluations). Day 8: 24 hours post Day 7 dose. Day 9: 48 hours post Day 7 dose (analyzed as part of scheduled hematology and clinical chemistry evaluations).
CCI [REDACTED]			X*		X*			X*	X*	X*				Days 1, 4, and 7: Predose. Day 8: 24 hours post Day 7 dose. Day 9: 48 hours post Day 7 dose.

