### 3.1.1. Part A (Single Ascending Dose)

Part A will comprise a single-dose, sequential group, escalating-dose design conducted in healthy adult male and female subjects; also incorporating a single-group, 2-period crossover arm investigating the effect of dosing AQ280 with food compared to dosing in the fasting condition. The first dose level administered is planned to be 3 mg AQ280.

A total of approximately 40 subjects are planned to be studied in 5 groups (Groups A1 to A5; with one of the groups including the food effect evaluation). In each group, 6 subjects will receive AQ280 and 2 subjects will receive placebo. The dose will be administered in the fasted state in accordance with the randomization schedule on the morning of Day 1 for all groups, including Period 1 for the food effect evaluation group (see [Section 3.1.1.1](#) for additional food-evaluation group requirements). Each group should contain both male and

female subjects, preferably at least 2 subjects of each gender. Additional groups may be added based on the need for more evaluations or groups removed based on data obtained.

The first group in Part A will be divided into 2 cohorts, with each cohort being dosed at least 24 hours apart. The first cohort will comprise 2 subjects, with 1 subject receiving AQ280 and 1 subject receiving placebo. The second cohort will comprise 6 subjects, with 5 subjects receiving AQ280 and 1 subject receiving placebo. The 2 sentinel subjects (first cohort) will be dosed at least 24 hours before the second cohort of 6 subjects. Dosing of subjects in the second cohort will not occur if any of the dose escalation stopping criteria are met by the 2 sentinel subjects.

There will be a minimum of 9 days between dose escalations for each group.

Potential subjects will be screened to assess their eligibility to enter the study from 2 days up to 5 weeks before the dose of AQ280 or placebo. Each subject will participate in 1 group only and will reside at the study site from Day -1 (the day before dosing) to Day 3 of the treatment period, with dose administration occurring on Day 1. A safety follow-up phone call will be conducted 1 week ( $\pm 2$  days) after dosing.

Each eligible subject will participate in 1 treatment period only, except for the food effect group, where each subject will participate in 2 treatment periods.

[figure not shown]
Based on the ongoing review of the safety, tolerability, and PK results, additional outpatient visits may be required.

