### 7.1.2. Calculation of the Summary Statistics

For continuous data the following rules will be applied:

- Missing values will not be imputed, unless specifically stated otherwise.
- Unrounded data will be used in the calculation of summary statistics.
- If the number of subjects with valid observations ( $n < 3$ ), summary statistics will not be calculated, with the exception of  $n$ , minimum, and maximum.
- In general, as early termination data are not associated with any scheduled timepoint, they will be excluded from all calculations of summary statistics and statistical analyses. Exceptions may be made where justified.

For categorical data the following rules will be applied:

- For ordered categorical data (eg, adverse event [AE] severity), all categories between the possible minimum and maximum categories will be included, even if  $n = 0$  for a given category.
- For non-ordered categorical data (eg, race), only those categories for which there is at least 1 subject represented will be included; unless specifically stated otherwise.
- Missing values will not be imputed, unless specifically stated otherwise. A ‘missing’ category will be included for any parameter for which information is missing. This will ensure that the population size totals are consistent across different parameters.

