DAUC T	h*ng/mL/mg	AUC T normalized by dose administered (Part B only)
DAUC 0-∞	h*ng/mL/mg	AUC 0-∞ normalized by dose administered
DC max	ng/mL/mg	C max normalized by dose administered

\* Units are based on concentration units (provided by the bioanalytical lab or preferred units for presentation of PK parameters) and dose units used in the study.

b The AUC will be calculated using the linear trapezoidal rule for increasing concentrations and the logarithmic rule for decreasing concentrations (linear up/log down rule).

c Based on the last observed quantifiable concentration

d Calculated by dividing the parameter by the dose (mg)

Additional PK parameters may be determined where appropriate.

Pharmacokinetic analysis will be carried out where possible using actual dose administered (mg) and actual postdose blood sampling times. If an actual time is missing, the sample concentration result will be treated as missing unless there is scientific justification to include the result using the nominal time.

The parameters  $C_{\max}$ ,  $C_{\text{trough}}$ ,  $t_{\text{last}}$ , and  $t_{\max}$  will be obtained directly from the concentration-time profiles. If  $C_{\max}$  occurs at more than 1 timepoint,  $t_{\max}$  will be assigned to the first occurrence of  $C_{\max}$ .

The metabolite:parent ratio(s) (MRAUC or MRCmax) will be calculated as follows:

$$MR_{AUC} = (AUC_{0-\infty} [AQ282] / MW [AQ282]) / (AUC_{0-\infty} [AQ280] / MW [AQ280]),$$

where MW is the molecular weight of each analyte

$$MR_{C_{max}} = (C_{max} [AO282] / MW [AO282]) / (C_{max} [AO280] / MW [AO280]),$$

where MW is the molecular weight of each analyte

The molecular weights of AQ280 and AQ282 to be used in the adjustment are as follows:

CCI

The parameter  $AUC_{0-t_{last}}$  or other common partial area may be used to determine  $MR_{AUC}$  if  $AUC_{0-\infty}$  cannot be reliably calculated for the majority of subjects.

The accumulation ratio(s) ( $AR_{AUC}$  and  $AR_{C_{max}}$ ) will be calculated as follows:

$$AR_{AUC} = AUC_{0-1} \text{ Profile Day 7} / AUC_{0-1} \text{ Profile Day 1}$$

$$AR_{C_{max}} = C_{max} \text{ Profile Day 7} / C_{max} \text{ Profile Day 1}$$

The linearity ratio (LR) will be calculated as ratio of  $AUC_{0-\tau}$  following multiple dosing to  $AUC_{0-\infty}$  following a single dose:

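### The ±10% sampling-time rule for the concentration summaries has no predose exception, no minimum early window and no late cap; it is unworkable for Part B predose samples and may drop Part A samples at 0.25 h and 0.5 h

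*SAP*

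**What the plan says.** The rule in SAP 7.5.2 opens: "If the actual time of sample collection deviates from the nominal time by more than"; the limit is one tenth of nominal time, in either direction. The consequence it sets for a sample outside that limit is that "the plasma concentration will be flagged and excluded from the summary statistics". Exclusion is automatic, whereas the vomiting rule in the same section only allows exclusion. Neither document gives a predose exception or any window in minutes for PK samples.

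The times it acts on are in Protocol Appendix 6. Part A has "Day 1: Predose, 0.25, 0.5, 1, 1.5, 2, 3, 4, 6, 8, and 12 hours postdose", then 24 and 36 h, and finally "Day 3: 48 hours postdose". Part B repeats the predose-to-12 h series on Days 1 and 7, with later samples after each, and adds "Days 3 through 6: Predose".

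Three other provisions matter:

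- **Parameters.** SAP 7.5.1: "Pharmacokinetic analysis will be carried out where possible using actual dose administered (mg) and actual postdose blood sampling times".
- **Group size.** SAP 3.1.1: "In each group, 6 subjects will receive AQ280 and 2 subjects will receive placebo". Under SAP 7.1.2, with fewer than 3 valid values "summary statistics will not be calculated, with the exception of" n, minimum and maximum.
- **Order of procedures.** Protocol 7.3.4.3 (continuous ECG, Part A) puts PK sampling after the ECG extraction window when the two coincide, and each extraction lasts 5 minutes. Protocol Section 7 ranks PK blood samples second only to dosing, ahead of other procedures such as ECGs.

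**The concern.** A tolerance proportional to nominal time vanishes at time zero, is very tight in the first half hour and becomes very wide at the end of the profile. The first two features can remove usable values from the concentration tables and from the mean figures that plot the same statistics.

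The predose gap matters most in Part B. Protocol 3.4 says Part B is meant to reach and hold steady state, and the SAP plans no formal steady-state analysis, so summaries of successive predose concentrations are natural evidence for it. On Day 1, predose values should be 0 and little is lost.

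The early gap matters because of the ECG instruction. Chance lateness would remove a value here and there, but a fixed order of procedures could delay every sample at a timepoint in the same way.

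**Working it through.** **Inputs.** Tolerance 10% (SAP 7.5.2); nominal times and ECG times (Protocol Appendix 6); extraction length 5 minutes (Protocol 7.3.4.3); 6 active subjects per group (SAP 3.1.1). The half-life is redacted in Protocol 3.4, so 3 to 24 h is assumed for illustration.

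**1. Windows.** Window = 0.10 × nominal time. The SAP states only the percentage, so there is no figure in minutes to reproduce.

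| Nominal time | Window either side | 5-minute delay as % of nominal |
|---|---|---|
| Predose (0 h) | 0 or undefined | undefined |
| 0.25 h (15 min) | 1.5 min | 33.3% |
| 0.5 h (30 min) | 3 min | 16.7% |
| 1 h (60 min) | 6 min | 8.3% |
| 12 h | 72 min | 0.7% |
| 24 h | 2.4 h | 0.3% |
| 48 h | 4.8 h | 0.2% |

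**2. Predose.** Ten percent of 0 is 0, and a percentage deviation from 0 is not defined, so the rule cannot be programmed sensibly. The Part B Day 2 sample escapes because it is labelled 24 h postdose (window 2.4 h). The samples on Days 3 to 7 are labelled predose, and the SAP does not say whether they carry a nominal time of 24 h after the previous dose.

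**3. ECG, then PK.** Appendix 6 schedules continuous ECG and PK sampling together at 0.25 h and 0.5 h in Part A. If extraction starts at the nominal time and blood is drawn as it ends, the delay is 5/15 = 33% and 5/30 = 17%. Both exceed 10% and are excluded. At 1 h it is 5/60 = 8.3% and the sample is kept.

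**4. Effect on the tables.** Summaries collapse to n, minimum and maximum once 4 of 6 values are lost. If breaches were independent with probability p, P(at least 4 of 6) is 1.7% at p = 0.2, 7% at 0.3 and 34% at 0.5. Independence does not describe step 3, where all 6 could be lost together.

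**5. What the early window means in concentration.** In a one-compartment oral model with assumed absorption rates of 0.5 to 4 per hour and half-lives of 3 to 12 h, a sample at 0.25 h is higher than its nominal value by about 5 to 9% if 1.5 minutes late, 7 to 12% if 2 minutes late, and 15 to 30% if 5 minutes late.

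**6. The late window.** Under log-linear decline, a sample 4.8 h late at 48 h is low by 1 − 2^(−4.8/half-life):

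| Assumed half-life | Late-edge sample low by |
|---|---|
| 3 h | 67% |
| 6 h | 43% |
| 12 h | 24% |
| 24 h | 13% |

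One such value among 6 otherwise equal ones lowers the mean by a sixth of that: 67/6 = 11% down to 13/6 = 2%.

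**The case against.** The strongest reply is that no endpoint depends on this rule. AUC, Cmax and accumulation ratios come from actual times, so dose proportionality and food effect are untouched. All concentrations are listed, and individual and overlay plots are planned. That stands and fixes the point as minor.

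A proportional tolerance also has a rationale during absorption: step 5 shows that a few minutes at 0.25 h is not negligible in concentration. That stands too. The defect is the absence of limits at either end and of a predose rule, not the use of a percentage as such.

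The ECG argument is conditional. It concerns Part A only and assumes extraction begins at the nominal time; a site could finish extraction before it, and Protocol Section 7 gives PK samples priority. The protocol also says these recordings will be archived without extraction in this study. Even so, the ordering instruction remains, and the two sections do not settle which procedure comes first.

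A reader might infer that the mean profiles will in fact keep badly distorted 48 h values. The documents do not support that: subjects are resident through 48 h, and the protocol asks for sampling close to nominal time. A reader might also take 303/35 × ln 2 = 6.0 h from the predicted exposures at 10 mg and quote 43% as the error. That treats predicted figures as a measured half-life and assumes instantaneous absorption with a single-phase decline, for an oral capsule. Only the range is defensible.

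**Conclusion.** The point holds as a minor defect in a descriptive rule. Two parts need action: the rule has no workable meaning for the Part B predose samples on Days 3 to 7, and at 0.25 h and 0.5 h in Part A it would systematically drop samples drawn after a 5-minute extraction that starts at the nominal time. The late window is a loose end: it permits up to 4.8 h at 48 h, worth 67% to 13% on a single late-edge value for an assumed half-life of 3 to 24 h, but such a deviation is unlikely.

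It would be wrong to conclude that the terminal phase or half-life will be misestimated. SAP 7.5.1 and 7.5.1.1 derive these from each subject's own profile at actual times. Nor is loss of whole summaries likely from scattered lateness alone; it becomes a real prospect only if the order of procedures delays every subject.

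**What to change.** Amend SAP 7.5.2 before database lock:

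- Treat a predose sample as valid for the summaries if it was taken before that day's dose.
- Add an absolute minimum window in minutes at the early timepoints, wide enough for the ECG-then-PK order, and a maximum window at the late ones.
- Keep flagging deviations in the listings.
- Reconcile Protocol Section 7 with Protocol 7.3.4.3 on the order of PK sampling and ECG extraction, and record the order actually used.

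The cost is a short SAP table and minor programming. The trade-off is a slightly wider timing tolerance in the early summaries: under the assumptions in step 5, a 5-minute delay at 0.25 h raises the value by 15 to 30%, so a footnote to the early means should state the window used.

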### **7.5.3. Pharmacokinetic Statistical Methodology**

#### **7.5.3.1. Dose Proportionality**

A statistical analysis will be conducted to investigate the dose proportionality of  $AUC_{0-t_{last}}$ ,  $AUC_{0-\infty}$ , and  $C_{max}$  for AQ280 and AQ282 on profile day 1 for Part A and  $AUC_{0-t}$  and  $C_{max}$  for AQ280 and AQ282 on profile day 7 for Part B.

The PK parameters will be analyzed using a power model that will have the following form:

$$parameter = intercept \times dose^{slope} \times random\ error$$

Using the natural log (ln) transformation, a power model can be expressed as a linear regression equation:

$$\ln(parameter) = intercept + slope \times \ln(dose) + random\ error$$

Dose proportionality holds if the slope of the regression line is close to 1. The estimate of the slope and its 95% confidence interval will be used to quantify the degree of non-proportionality. For each PK parameter separately, a pooled estimate (across all doses) of slope, corresponding 95% confidence interval (CI), and between-subject coefficient of variation (CV) will be calculated. Figures (on the logarithmic-logarithmic scale) containing individual values, the power model line (95% CI), and the dose proportionality line (defined as the power model line with slope of 1) will be created for each PK parameter. Additionally, figures (on the logarithmic-linear scale) containing individual values and geometric means will be created for each corresponding PK parameter normalized by dose administered.

The lack of fit test will be conducted for the statistical assessment of linearity assumption, and thus appropriateness of a power model. The lack of fit model will be the same as the power model fitted, but with dose included as an additional fixed effect. The statistical

assessment will rule the linearity assumption acceptable if the diagnostic plots appear reasonable and the lack of fit 2-sided p-value  $>0.05$  (dose effect is not significant at the 0.05 level of significance). The assessment of linearity assumption may also occur via visual examination of the figures by the pharmacokineticist. This assessment may override the statistical assessment; where this occurs, it will be detailed in the CSR.

If the assumption of linearity is ruled acceptable and the 95% CI for the slope spans 1, it will be deemed that there is no statistical basis to conclude a lack of proportionality.

If the assumption of linearity is ruled unacceptable for any PK parameter, its corresponding PK parameter normalized by dose administered will be ln-transformed and analyzed using an analysis of variance (ANOVA) model. The model will include dose as a factor.

For each PK parameter separately, the geometric least squares mean (GLSM) for each dose, p-values for the overall, and pairwise dose comparisons will be calculated. Residual plots will be produced to assess the adequacy of the model(s) fitted.

Caution should be used when interpreting results from the statistical analyses conducted in this study because no adjustment for multiple comparisons will be performed.

Examples of the SAS code that will be used are as follows:

